### Variables

*Please list each research question included in this study.*

1. Is CET a feasible and acceptable intervention for caregivers and their children with ADHD? Is its feasibility and acceptability comparable to the current gold-standard psychosocial treatment for ADHD (BPT)?
2. Does CET improve working memory in children with ADHD, and are these improvements superior to those found for BPT (which is not expected to improve working memory)?
3. Does CET improve ADHD symptoms in children with ADHD, and are these improvements non-inferior to improvements associated with gold-standard BPT?
4. (Fidelity Check) Does BPT improve oppositional-defiant symptoms in children with ADHD, and how does CET compare to BPT for these expected improvements?

### Analysis Plan

Hypotheses	
For each of the research questions listed in the previous section, provide one or multiple specific and testable hypotheses. Please state if the hypotheses are directional or non-directional. If directional, state the direction. A predicted effect is also appropriate here.
 
Primary Outcome
 
1. Near-transfer: Central executive training (CET) will produce greater improvements than behavioral parent training (BPT) on the Rapport phonological (PH) and visuospatial (VS) working memory tests (2 group x 2 task x 2 time points (pre, post)). Critical test is the group x time interaction. The 2 tasks are included in the omnibus ANOVA to (1) address recommendations to probe cognitive abilities using multiple tests, and (2) maximize power for the critical group x time interaction. The 2 working memory tests are considered to tap the same 'central executive' working memory; they differ in whether that central executive is processing phonological or visuospatial information. If the group x time interaction is significant at <math>p = .05</math> or less, it will be followed by Bonferroni-corrected within-group post-hocs for each task and ANCOVA of post-treatment covaried for pre-treatment separately for each task (i.e., residualized gain scores). These post-hocs will also be performed if the main effect of time is significant (but not the group x time interaction) to allow us to better characterize change within each group (i.e., did each treatment produce significant change?). Stimuli correct per trial will be used.

------------	--

Statistical models
Transformations
Follow-up analyses
Inference criteria
Data exclusion
Missing data
Exploratory analysis

## Secondary Outcomes

2. Far-transfer subjective ADHD symptoms: BPT and CET will both show significant reductions in ADHD symptoms measured by unblinded parent ratings. Two scales are used: the norm-referenced BASC-2 (T-scores based on age and gender norms) and CSI-IV (raw symptom severity scores). Both have separate Attention Problems and Hyperactivity/Impulsivity subscales. Both will be tested via 2 group x 2 subscale x 2 time point mixed-model ANOVA. Critical test is the group x time interaction for both. Post-hoc plan follows #1 above.
3. Far-transfer objective (proximal) ADHD symptoms: CET will show greater reductions in actigraph-measured hyperactivity than BPT during the Rapport PH and VS working memory tests. Same 2 group x 2 task (PH-actigraphy, VS-actigraphy) x 2 time points approach as above; same post-hoc plan. Critical test is the group x time interaction. Actigraph data will be PIM intensity scores, summed across 3 actigraphs (non-dominant wrist, left ankle, right ankle).
4. Far-transfer objective (distal) ADHD symptoms: CET will show greater reductions in actigraph-measured hyperactivity than BPT during the low cognitive load Painting tasks at the beginning and end of each testing session. Same 2 group x 2 task (PaintBeginning-actigraphy, PaintEnd-actigraphy) x 2 time points approach as above; same post-hoc plan. Critical test is the group x time interaction. Actigraph data will be PIM intensity scores, summed across 3 actigraphs (non-dominant wrist, left ankle, right ankle).
5. Far-transfer subjective oppositional-defiant symptoms: BPT will show greater improvements in unblinded parent reports of oppositional defiant symptoms on the CSI-IV. Only the ADHD and ODD sections of the CSI-IV were administered. Analysis will be 2 group x 2 timepoints mixed-model ANOVA. Critical test is the group x time interaction. CSI-IV raw symptom scores for the ODD dimension will be used as dependent variable. Bonferroni-corrected paired-sample t-tests for each group separately (pre vs. post), and between-group at post covaried for pre-treatment ODD symptoms are tested because of compelling evidence that BPT improves these symptoms (manipulation check; if no significant reductions in BPT group, may indicate limited BPT efficacy).
6. Client Satisfaction Questionnaire-8 (CSQ-8) parent report at post-treatment (total scores) will be compared across groups (BPT vs. CET). No significant differences expected.
7. Barriers to Treatment Participation Scale (BTPS) parent report at post-treatment (total scores and all subscales). No significant differences are expected. The Relevance of Treatment subscale will be interpreted as evidence of intervention expectancies.
8. CET only: System Usability Scale (SUS). Child reported feasibility of CET system. Expected to be high (mean of at least 3.5 on 5-point Likert scale, where higher scores indicate better usability).
9. CET training duration. Total minutes trained and total training games completed will be reported. Descriptive; no hypotheses are offered.

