## Sample size

*Describe the sample size of your study. How many units will be analyzed in the study? This could be the number of people, birds, classrooms, plots, interactions, or countries included. If the units are not individuals, then describe the size requirements for each unit. If you are using a clustered or multilevel design, how many units are you collecting at each level of the analysis?*

The final analyzed sample size is expected to be BPT = 27, CET = 27. BPT collection is complete; the last CET group is anticipated to be complete in May/June 2017.

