#### Feasibility/Acceptability Outcomes

6. Client Satisfaction Questionnaire-8 (CSQ-8) parent report at post-treatment (total scores) will be compared across groups (BPT vs. CET) using independent samples T-test.

7. Barriers to Treatment Participation Scale (BTPS) parent report at post-treatment (total scores and all subscales). Independent samples t-tests. The Relevance of Treatment subscale will be interpreted as evidence of intervention expectancies.

8. CET only: System Usability Scale (SUS). Child reported feasibility of CET system. Expected to be high (mean of at least 3.5 on 5-point Likert scale, where higher scores indicate better usability). Descriptive statistics only.

9. CET training duration. Total minutes trained and total training games completed will be reported. Descriptive statistics only.

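### The plan asks whether CET is as acceptable as BPT but gives no rule for concluding so: the only between-arm analyses of the CSQ-8 and BTPS test for a difference, with 27 per arm

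*Combined protocol and SAP*

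**What the plan says.** The first research question (Variables) has two halves. One asks whether CET is feasible and acceptable in itself. The other is comparative: "Is its feasibility and acceptability comparable to the current gold-standard psychosocial treatment for ADHD (BPT".

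The comparative half rests on two parent questionnaires collected only at post-treatment. In the hypotheses (Secondary Outcomes, item 6), CSQ-8 totals "will be compared across groups (BPT vs. CET). No significant differences expected". Item 7 says of the BTPS: "No significant differences are expected. The Relevance of Treatment subscale will be interpreted as evidence of intervention expectancies".

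The analysis plan (Feasibility/Acceptability Outcomes) says that CSQ-8 totals "will be compared across groups (BPT vs. CET) using independent samples T-test", and for the BTPS it gives "parent report at post-treatment (total scores and all subscales). Independent samples t-tests". The BTPS has a total and four subscales, so with the CSQ-8 total there are six comparisons. The System Usability Scale and training duration are CET-only and descriptive.

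Three other provisions bear on these tests:

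- Covariates and Data Handling turns independent-samples t-tests into ANCOVAs if pre-treatment group differences call for covariates.
- Inference criteria sets p at .05 or lower and a Bayes factor of 3 or greater. It reports BF10 or BF01, whichever exceeds 1, and makes p-values primary when the two disagree. It does not say whether tests are one- or two-sided.
- Sample size states: "The final analyzed sample size is expected to be BPT = 27, CET = 27". The rationale is recruitment dates and software readiness; there is no power calculation.

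**The concern.** A test for a difference is not designed to answer a question about comparability. If the registered prediction is that no significant difference will be found, it is met whenever p exceeds .05, and a small sample makes that outcome more likely whatever the truth. No margin says how much worse CET could be and still count as comparable, and no rule ties the conclusion to a confidence interval or to BF01.

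Two things are at stake. The first is the answer to a stated research question: CET could be noticeably less acceptable to parents and the prediction would still often be met. The second is the Relevance subscale, which the plan takes as evidence on expectancies. Several symptom outcomes are unblinded parent ratings in a non-randomized comparison, so a difference in expectancies, in either direction, is a rival explanation that a non-significant test cannot dismiss.

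**Working it through.** The documents give no power, SD or margin for these scales, so there is no plan figure to reproduce.

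**Inputs.** From the plan: n = 27 per arm (Sample size); alpha = .05 (Inference criteria); independent-samples t-test (Feasibility/Acceptability Outcomes). Assumed: two-sided testing, no covariates, and true differences d in SD units chosen for illustration.

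**Step 1: chance of a non-significant result.** Degrees of freedom are 2 × 27 − 2 = 52. The noncentrality parameter is d × √(27/2) = d × √13.5; at d = 0.5 it is 1.837. The chance of p > .05 comes from the noncentral t distribution.

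| True difference | Chance of p > .05 |
|---|---|
| 0 | 95% |
| 0.3 SD | 81% |
| 0.4 SD | 70% |
| 0.5 SD | 56% |
| 0.6 SD | 42% |
| 0.8 SD | 18% |

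A simulation of 200,000 trials at 0.5 SD also gave 56%. One-sided testing at .05 would give 43% at 0.5 SD. The plan states no multiplicity correction for these tests; Bonferroni over all six would give 81% at 0.5 SD. The difference detectable with 80% power is 0.78 SD.

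**Step 2: what a non-significant result leaves open.** The standard error in SD units is √(2/27) = 0.272. The 95% interval half-width is 0.546 SD, so an observed gap of up to about 0.55 SD is non-significant. Even an observed gap of zero leaves 0.5 SD inside the interval.

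**Step 3: what the Bayes factor adds.** The plan names JASP but no prior, so a default Cauchy prior with scale 0.707 is assumed. With 27 per arm BF01 cannot exceed 3.65, and it reaches 3 only if the observed gap is within about 0.19 SD. That happens about 51% of the time with no true difference and 12% with a true 0.5 SD difference. The result is non-significant with BF01 below 3 in about 95% − 51% = 44% of trials under no difference, and 56% − 12% = 44% under a 0.5 SD difference. The plan does not say what is concluded in that zone, beyond p-values being primary if the two count as discrepant.

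**Step 4: a margin rule for comparison.** Require the CET-worse bound of the 90% interval (one-sided .05, half-width 0.456 SD) to lie inside a margin. With no true difference, margins of 0.5, 0.6 and 0.7 SD are met about 57%, 70% and 81% of the time. With a true 0.5 SD deficit, the 0.5 SD margin is wrongly met about 5% of the time.

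**The case against.** The strongest reply is that the plan claims less than the concern implies. It poses a question and states an expectation; it does not say that p > .05 on the CSQ-8 or BTPS establishes comparability. A reader might infer otherwise from Recommended elements, where a null result is said to indicate equivalence. That sentence concerns the residualized-gain test, which needs a pre-treatment score on the same scale, and neither questionnaire has one. Likewise, the plan does not say that a non-significant Relevance comparison means equal expectancies. These points stand, and they rule out the charge that the plan defines non-significance as proof. They do not supply another rule: "No significant differences are expected" is the only comparative prediction offered.

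Second, BF01 is a planned measure of evidence for no difference, and under the assumed prior a threshold of 3 separates the two cases (51% against 12%) not much worse than a 0.5 SD margin does (57% against 5%). It would therefore be wrong to say that the plan relies on p-values alone or has no suitable tool. What is missing is the rule: nothing requires BF01 of 3 or more before comparability is concluded.

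Third, a reader might infer that these scores cannot be adjusted for pre-treatment differences. They can, through the covariate provision. Adjustment could shift the percentages above, but an ANCOVA is still a test for a difference without a margin.

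Finally, these are secondary outcomes, and the first half of the question, partly addressed by the usability benchmark and training duration, is untouched. That limits the weight of the point.

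**Conclusion.** The point holds as a missing decision rule. The plan asks about comparability, analyses it only with tests for a difference, and gives no criterion other than the absence of significance. Under unadjusted two-sided testing with 27 per arm, the registered prediction is met 95% of the time if the arms are equal and 56% of the time if they truly differ by 0.5 SD. The SD values, the sidedness and the Bayes prior are assumptions, and covariate adjustment or a multiplicity correction would move the figures. Across the illustrative range of 0.3 to 0.6 SD the miss rate runs from 81% to 42%, so the conclusion does not hang on one value. The wording should be changed; the primary working-memory analysis is not affected.

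**What to change.** Amend items 6 and 7 in both Secondary Outcomes and Feasibility/Acceptability Outcomes so that the prediction of no significant difference is no longer the basis for comparability:

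1. For CSQ-8 total and BTPS total, report the CET minus BPT difference (covariate-adjusted if covariates are triggered) with its confidence interval, and state for each scale which direction is worse for CET.
2. Conclude that CET is comparable only if the CET-worse bound of the 90% interval (one-sided .05) lies inside a margin in scale points. The co-PIs without data access, who already make the data-handling decisions, should fix and justify it.
3. Where the margin is not met, conclude that CET is worse only if the 95% interval excludes zero, which keeps the threshold at .05 two-sided. Otherwise state that the result is inconclusive.
4. Report BF01 alongside, with its prior stated, as supporting evidence.
5. For the Relevance subscale, report the two-sided interval and do not read p > .05 as equal expectancies; a difference in either direction matters there.

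The change costs wording and a few intervals, with no new data. The downside is a less favourable statement: with no true difference, a 0.5 SD margin would fail about 43% of the time (100% − 57%) and a 0.7 SD margin about 19% (100% − 81%). In return, a false finding of comparability at a true 0.5 SD deficit would fall from 56% to about 5% with the 0.5 SD margin. The rule does nothing about the period and site confounding of a sequential, non-randomized design, and the report should say so.

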## Recommended elements

1. All hypothesized interactions are expected to look like Figure 1 in Redick (2015). In other words, no pre-treatment group differences, and differential improvements favoring the group hypothesized to improve. Should pre-treatment group differences be observed, differential improvements favoring the group hypothesized to improve would be observed when using post-treatment covaried for pre-treatment analysis (residualized gain scores). No differences in this test indicate equivalence between interventions.
2. P-values and Bayes Factors will be reported. P-values will be considered primary in cases of discrepant results (to follow current conventions in the field). P-values of .05 or less will be considered significant (after Bonferroni corrections for post-hoc tests). Bayes Factors of 3 or greater will be considered significant.

## Sampling Plan

### Existing Data

*Preregistration is designed to make clear the distinction between confirmatory tests, specified prior to seeing the data, and exploratory analyses conducted after observing the data. Therefore, creating a research plan in which existing data will be used presents unique challenges. Please select the description that best describes your situation. Please do not hesitate to contact us if you have questions about how to answer this question ([contact]).*

Registration prior to accessing the data

### Explanation of existing data

*If you indicate that you will be using some data that already exist in this study, please describe the steps you have taken to assure that you are unaware of any patterns or summary statistics in the data. This may include an explanation of how access to the data has been limited, who has observed the data, or how you have avoided observing any analysis of the specific data you will use in your study. The purpose of this question is to assure that the line between confirmatory and exploratory analysis is clear.*

The data exists in pieces on the PI's lab server, and we have begun to collate them into a united dataset that will be used

for analyses. All data handling decisions were made by Co-PIs without access to the data, most of whom are at different universities. The primary and secondary outcomes to be reported in this study were determined by Co-PIs without access to the data.

## Data collection procedures

*Please describe the process by which you will collect your data. If you are using human subjects, this should include the population from which you obtain subjects, recruitment efforts, payment for participation, how subjects will be selected for eligibility from the initial pool (e.g. inclusion and exclusion rules), and your study timeline. For studies that don't include human subjects, include information about how you will collect samples, duration of data gathering efforts, source or location of samples, or batch numbers you will use.*

### Description of essential elements

Preregistration is for data analysis; data collection is almost complete. All outcome measures and analyses were selected without access to the data.

#### Study Timeline

Children were not randomized to treatment condition. Families recruited between June 2013 and December 2014 were offered behavioral parent training (BPT). The final BPT post-treatment session was completed in June 2015. Families recruited between June 2015 and December 2016 were offered central executive training (CET). The final CET post-treatment session was completed in [TBD, likely May/June] 2017. Recruitment to CET was closed when the software for the active comparator was completed. We are currently conducting a pilot randomized trial of CET versus this active comparator (inhibition training).

Identical procedures were used for both samples. Both treatments were delivered in small group format (2-4 families) or individually as needed to accommodate families' schedules. Schedule changes were accommodated to the extent possible (e.g., make-up sessions the same week).

#### Inclusion/Exclusion Criteria

All children and caregivers completed an identical evaluation, regardless of group assignment, that included detailed, semi-structured clinical interviewing (K-SADS; Kaufman et al., 1997). The K-SADS (2013 Update) assesses developmental history as well as onset, course, and impairment of DSM-5 (APA, 2013) disorders in children and adolescents. Parent and teacher ADHD ratings were obtained from the Behavior Assessment System for Children (BASC-2; Reynolds & Kamphaus, 2004) and Child Symptom Inventory (CSI-IV; Gadow & Sprafkin, 2002).

Study eligibility required all of the following (1) DSM-5 diagnosis of ADHD (any presentation) by the directing clinical psychologist based on K-SADS; (2) Borderline/clinical elevations on at least one parent and one teacher ADHD rating scale. A previous diagnosis of ADHD was also sufficient for inclusion. All children had current impairment (K-SADS). Comorbidities reflect clinical consensus best estimates. Positive screens for learning disabilities will be based on score(s) 1 SD or more below age-norms on one or more Kaufman (KTEA-2/3; 2004, 2014) academic skills battery subtests.

Medication rates will be reported. Psychostimulants were withheld for at least 24-hours prior to all research testing sessions (i.e., all working memory performance and actigraph hyperactivity data was collected off-medication).

Following convention in our assessment clinic, children prescribed psychostimulants received their usual dose during the baseline psychoeducational assessment (IQ, achievement testing) to provide the best estimates of their child's skills/abilities in the psychoeducational report provided to parents. Changes in medication status during treatment will be reported.

Children were excluded for gross neurological, sensory, or motor impairment; seizure disorder, psychosis, or intellectual disability; or non-stimulant medications that could not be withheld for testing. No inclusion/exclusion based on working memory/executive functioning performance was set.

#### Procedures

Pre-treatment testing occurred during a larger battery of two, 3-hour sessions. Post-testing occurred during a single, 3-hour session. A 90-minute mid-treatment testing session was conducted for children in the BPT group. As specified in the NIH R34 proposal, no mid-treatment sessions were completed for the first CET groups. This design difference was considered acceptable because it favored the null (i.e., test-retest effects, if present, would favor the BPT group). Statistical tests will therefore assess pre-post changes.

All tests were counterbalanced within/across sessions to minimize order/fatigue effects. Children received brief breaks after each task, and preset longer breaks every 2-3 tasks to minimize fatigue.

no file selected

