#### Primary Outcome

1. Near-transfer: 2 group x 2 task x 2 time points (pre, post). Tasks are Rapport phonological (PH) and visuospatial (VS) working memory tests. Critical test is the group x time interaction. The 2 tasks are included in the omnibus ANOVA to (1) address recommendations to probe cognitive abilities using multiple tests, and (2) maximize power for the critical group x time interaction. The 2 working memory tests are considered to tap the same 'central executive' working memory; they differ in whether that central executive is processing phonological or visuospatial information. If the group x time interaction is significant at  $p = .05$  (or lower), it will be followed by Bonferroni-corrected within-group post-hocs for each task and ANCOVA of post-treatment covaried for pre-treatment separately for each task (i.e., residualized gain scores). These post-hocs will also be performed if the main effect of time is significant (but not the group x time interaction) to allow us to better characterize change within each group (i.e., did each treatment produce significant change?). Stimuli correct per trial will be used.

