#### Recommended elements

10. All hypothesized interactions are expected to look like Figure 1 in Redick (2015). In other words, no pre-treatment group differences, and differential improvements favoring the group hypothesized to improve. Should pre-treatment group differences be observed, differential improvements favoring the group hypothesized to improve would be observed when using post-treatment covaried for pre-treatment analysis (residualized gain scores). No differences in this test indicate equivalence between interventions.

11. P-values and Bayes Factors will be reported. P-values will be considered primary in cases of discrepant results (to follow current conventions in the field). P-values = .05 or lower will be considered significant (after Bonferroni corrections for post-hoc tests). Bayes Factors = 3 or greater will be considered significant.

no file selected

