## Data exclusion

*How will you determine which data points or samples (if any) to exclude from your analyses? How will outliers be handled?*

Outliers (3 SD or more beyond group mean) will be windsorized relative to the group mean. Group = BPT or CET.

Attrition: If available, mid-treatment data will be substituted for missing post-treatment data. If not available, the most proximal (non-pre-treatment) data point for that child will be substituted. If not available, single imputation will be used based on all available demographic and performance data.

Duplicate Data: In cases of duplicate data with different administration dates, the first administration will be used unless there is compelling reason to select differently. If a child has duplicate task data from the same date, the file will be checked for notes (e.g., first administration was invalidated by fire alarm/child had to go to the bathroom). The first administration will be used unless there is a clear documented reason to select otherwise. If a participant has duplicate rating scale data from the same date (e.g., mom and dad filled out forms separately), we will select the rater who completed forms at the other time point. Priority will be given to ratings from the caregiver involved in treatment. Maternal ratings will be prioritized if no other distinguishing criteria are met. All decisions will be made without looking at the scores.

No checks will be performed to determine eligibility for inclusion in data analyses besides verification that each participant was consented and enrolled.

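### BPT children were tested mid-treatment and the first CET groups were not; the plan's favoring-the-null defence covers only a positive CET superiority claim, and no exposure-matched sensitivity analysis is specified

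*Combined protocol and SAP*

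**What the plan says.** The Procedures section records unequal testing. For one arm, "A 90-minute mid-treatment testing session was conducted for children in the BPT group"; for the other, "no mid-treatment sessions were completed for the first CET groups". It gives the direction of any resulting bias and accepts it: "This design difference was considered acceptable because it favored the null (i.e., test-retest effects, if present, would favor the BPT group". It then concludes: "Statistical tests will therefore assess pre-post changes".

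The primary analysis (Analysis Plan, Primary Outcome) follows that decision: "Near-transfer: 2 group x 2 task x 2 time points (pre, post", with the group x time interaction as the critical test. Within-group post-hoc tests for each task follow a significant interaction, or a significant main effect of time alone, to show whether each treatment produced change.

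The only stated use of mid-treatment scores is under Data exclusion: "If available, mid-treatment data will be substituted for missing post-treatment data". No comparison matched on number of exposures is specified, and no exploratory analysis is listed.

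Three other statements bear on the point:
- Research question 2 asks of CET: "are these improvements superior to those found for BPT (which is not expected to improve working memory".
- The Recommended elements say of the post-treatment comparison covaried for pre-treatment: "No differences in this test indicate equivalence between interventions".
- Study Timeline and Study design both say that procedures were identical in the two samples, which does not fit the Procedures section.

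**The concern.** Leaving the mid-treatment time point out of the model does not undo the extra testing, because the BPT post-score still comes after it. If the session included the working memory tasks, BPT children took them for the third time at post-treatment, and CET children without the session for the second time. Any further practice gain then sits in the BPT pre-post change and is subtracted from the CET advantage.

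The plan's defence is valid for one inference, a significant result favoring CET on working memory. The same data serve three other purposes that it does not cover:
- **The size of the CET effect.** The estimate would be pulled down by this source.
- **The within-BPT post-hoc tests.** An apparent working memory gain in BPT could be repeated testing, in an arm that the plan does not expect to improve.
- **A null result read as equivalence.** Bias towards no difference is then anti-conservative. The covaried comparison carries the same imbalance as the interaction.

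**Working it through.** The plan states no power, effect size, standard deviation or practice gain, and the sample size rationale is logistical. There is no figure of the plan's own to reproduce. What follows is a sensitivity calculation only.

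**Inputs from the documents**
- 27 children per arm (Sample size).
- Significance at .05, no correction for omnibus tests (Inference criteria). Sidedness is not stated; two-sided is assumed.
- 1-3-week test-retest reliability of .76 to .90 (Primary Outcomes, Working Memory). This is a correlation and says nothing about mean practice gain.
- Three CET waves of about 9 children (CET beta testing). The documents do not say which waves had no mid-treatment session.

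**Assumptions**
- The group x time test is treated as a two-sample t-test on change scores, df = 52.
- The pre-post correlation r equals the stated reliability, although the treatment interval is longer than 1-3 weeks.
- g is the extra gain from second to third exposure, in baseline SD; 0.10 and 0.20 are used.
- f is the share of CET without a mid-treatment session; 1/3, 2/3 and 1 are used.
- The mid-treatment session included the working memory tasks.

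**Formulas**
- SD of change = sqrt(2(1 - r)): sqrt(0.48) = 0.693 at r = .76; sqrt(0.20) = 0.447 at r = .90.
- Difference with 80% power at 27 per arm (noncentral t) = 0.777 SD of change: 0.777 x 0.693 = 0.538 baseline SD at r = .76; 0.777 x 0.447 = 0.347 at r = .90.
- Expected contrast = D - f x g, where D is the true CET effect. Noncentrality = (contrast / SD of change) x sqrt(27/2).

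Worked case: r = .76, g = 0.10, f = 1. The contrast is 0.538 - 0.100 = 0.438; divided by 0.693 this is 0.633; times 3.674 gives 2.32; power is 63%.

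**Power when D is set at 80% power without the imbalance**

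| r | g | f = 1/3 | f = 2/3 | f = 1 |
|---|---|---|---|---|
| .76 | 0.10 | 75% | 69% | 63% |
| .90 | 0.10 | 72% | 62% | 51% |
| .76 | 0.20 | 69% | 56% | 42% |
| .90 | 0.20 | 62% | 41% | 22% |

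The loss depends on the anchor. With D fixed at 0.5 SD, g = 0.10 and f = 1, power goes from 74% to 55% at r = .76, but only from 98% to 90% at r = .90.

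**No true CET effect** (r = .76, f = 1). The chance of a false finding for CET falls from 2.5% to 0.7% (g = 0.10) or 0.1% (g = 0.20). The chance of a false finding for BPT rises from 2.5% to 7.5% or 18%. This agrees with the plan that the imbalance is conservative for CET, and shows that it is not neutral for BPT.

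**The case against.** The plan discloses the imbalance, its direction and its reason. Research question 2 and the primary hypothesis concern CET superiority, and for that claim the imbalance costs power without inflating a false finding for CET. This stands, so an added analysis is supportive and does not correct an invalid test.

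A reader might make several stronger inferences that the documents do not support:
- **That the plan ignores its mid-treatment data.** It does not; they are the first substitute for missing post-treatment scores. They are unused only as an exposure-matched comparator.
- **That a third working memory exposure is established.** The content of the session is not listed, and at 90 minutes it was half as long as the 3-hour post-treatment session. The substitution rule makes working memory scores there plausible, not certain.
- **That the whole retest gain is subtracted from CET.** Only the second-to-third increment is at stake, and only for CET children without the session. The f = 1 column is the extreme case.
- **That the CET estimate is too low overall.** The comparison is sequential, non-randomized and spans institutions, so the net direction of bias is unknown.
- **That BPT mid-to-post change measures the retest gain directly.** It also contains elapsed time and treatment.

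The equivalence link also has limits. The sentence concerns the covaried comparison, introduced for the case of pre-treatment differences, and not the primary interaction. Reading non-significance as equivalence is a fault with or without the mid-treatment session; the imbalance makes it worse.

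**Conclusion.** The point holds in a limited form. The testing imbalance is real and the plan itself says which arm it would favor. Its defence does not extend to the effect estimate, the within-BPT post-hoc tests or a null read as equivalence. Whether working memory is affected depends on the undocumented content of the mid-treatment session.

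If it is, the downward shift in the contrast is f x g: from 0.033 SD (one third of CET, g = 0.10) to 0.20 SD (all of CET, g = 0.20) over the range tabulated. At g = 0.10, an effect otherwise detectable with 80% power has power of 51% to 75%. These figures rest on assumed values of g and f, on a short-interval reliability carried over to a longer interval, and on an effect placed exactly at 80% power. They show that the issue can matter at 27 per arm. They do not estimate its size in this study. The point should be settled before the data are analyzed.

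**What to change.** Keep the pre-post test as primary, and make these changes:

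1. In Procedures, state which tests were given at mid-treatment and which CET children had that session. Reconcile this with the statements in Study Timeline and Study design that procedures were identical.
2. If working memory was tested, pre-specify in the Primary Outcome section a supportive sensitivity analysis: CET pre-to-post, in children without a mid-treatment session, against BPT pre-to-mid. Both are then second exposures.
3. Report BPT mid-to-post change descriptively, as an upper guide to the retest increment that also contains time and treatment effects.
4. Limit the favoring-the-null statement to the working memory superiority claim.
5. Do not read a non-significant result as equivalence, whether or not the sensitivity analysis agrees. Two non-significant tests without a margin still do not show equivalence.

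The cost is wording and one more analysis of data already collected. The downside is that BPT pre-to-mid covers a shorter interval and only part of the treatment, so the comparison could favor CET if scores rise with time. Splitting CET by mid-treatment session may also coincide with software version and leave small groups, about 9 or 18 children if the split follows the waves. For both reasons the analysis should support the primary test and not replace it.
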